10.2. Sample Size Calculations

The primary outcome is the change in I-PSS total score between baseline and 12 months. The trial is powered to test the non-inferiority (NI) of each experimental arm to the TURP arm in terms of I-PSS. The three null hypotheses to be tested are:

- The mean difference in 12-month I-PSS total score (adjusted for baseline) between PUL and TURP is > 3
- ii. The mean difference in 12-month I-PSS total score (adjusted for baseline) between Rezum and TURP is > 3
- iii. The mean difference in 12-month I-PSS total score (adjusted for baseline) between iTIND and TURP is > 3

To test each hypothesis, participants will be pooled across the following randomisation schemes:

i. TURP vs PUL ii. TURP vs Rezum		iii. TURP vs iTIND
TURP: PUL: Rezum: iTIND	TURP: PUL: Rezum: iTIND	TURP: PUL: Rezum: iTIND
TURP: PUL: Rezum	TURP: PUL: Rezum	TURP: PUL: iTIND
TURP: PUL: iTIND	TURP: Rezum: iTIND	TURP: Rezum: iTIND
TURP: PUL	TURP: Rezum	TURP: iTIND

In data from the UNBLOCS trial (NIHR HTA 12-35-15) [33] the standard deviation (SD) of the I-PSS score at 12-months follow-up was 6.3 (based on the non-catheterised participants with complete data).

A non-inferiority margin of three points is used. This represents the minimally clinically important difference (MCID) for the outcome. [4,46,47] The non-inferiority hypothesis is equivalent to ruling out TURP providing an improvement of the MCID or greater against a minimally invasive treatment.

Assuming a minimally invasive arm has the same mean I-PSS as TURP, standard non-inferiority sample size formula suggests we would require 12-month information on 100 participants per intervention for each comparison for 90% power to conclude non-inferiority at a one-sided type I error rate of 0.0195 (nQuery). This p-value threshold yields a maximum chance of falsely concluding non-inferiority of 5% assuming a Dunnett correction.

We have inflated this sample size to account for a 25% attrition rate, which was seen in UNBLOCS for patient-reported outcomes. This gives a sample size of 134 participants per intervention for each comparison. Since we are adjusting for baseline I-PSS, we would expect power to be higher than 90%.

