The main analysis will be carried out in the per-protocol population. A linear mixed-effects model (mixed model for repeated measures) will be fitted to the six- and twelve-month I-PSS total score data, with fixed effects for baseline I-PSS, randomisation scheme, and a treatment-by-time interaction term. Random effects for site (this will be the Hub where a Hub and Spoke model is used) and individual (nested within site) will be used. Where required, the model will be weighted using the weights calculated as described above.

The estimated difference between control and each experimental treatment at 12 months will be extracted from the model and reported with 95% confidence intervals. Adjusted 95% CI will also be provided as supplementary information. The one-sided p-value for non-inferiority (with margin three) will be calculated. The critical p-value threshold will be set as 0.0195 so that the maximum chance of incorrectly concluding an arm is non-inferior when they all are inferior is 5% (following the Dunnett procedure).

The experimental arms will be compared to one another for the primary outcome, although the trial is not powered for this comparison.

²The hypothetical strategy targets the treatment effect in the hypothetical setting where the intercurrent event did not occur

Sensitivity analyses

Where IPW methods are used for the main analysis the analysis will be repeated without the use of IPW methods.

Supplementary analyses

Analyses will be repeated in the as-treated, modified ITT and ITT populations. We will also estimate the Complier Average Causal Effect (CACE) using Instrumental Variable (IV) methods.

We will also repeat the main analysis but with participants pooled across all 11 randomisation schemes. Appropriate methods, e.g. weighting procedures, will be used to account for any differences in patient-level variables between arms.

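### The 0.0195 threshold caps the family-wise error at 5% only if nearly all TURP men are shared by the three comparisons; under the protocol's pooling rule the cap is 5.74%

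*Protocol*

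**What the plan says.** Section 10.2 sets three non-inferiority hypotheses, one per minimally invasive treatment (MIT): "The trial is powered to test the non-inferiority (NI) of each experimental arm to the TURP arm in terms of I-PSS". On the margin it says "A non-inferiority margin of three points is used". The sample size uses a one-sided level of 0.0195 per comparison, and of that level the section says: "This p-value threshold yields a maximum chance of falsely concluding non-inferiority of 5% assuming a Dunnett correction".

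Section 10.3.1 makes the same number the decision rule: "The critical p-value threshold will be set as 0.0195 so that the maximum chance of incorrectly concluding an arm is non-inferior". The ceiling it gives there is again 5%, for the case where none of the three treatments is truly non-inferior, with Dunnett named as the method.

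The data for each test are also fixed in section 10.2: "To test each hypothesis, participants will be pooled across the following randomisation schemes", followed by a table of four schemes per comparison. Section 7.2.1 lists 11 schemes with equal allocation within each; seven contain TURP. Section 10.2 acknowledges that some participants will be absent from some of the analyses, but draws no consequence for the threshold.

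On intervals, section 10.3.1 says the 12-month differences "will be extracted from the model and reported with 95% confidence intervals". It adds that adjusted 95% intervals will be given as a supplement, without saying how they are built.

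**The concern.** Dunnett's threshold is less strict than one for independent tests because a common control group makes the three estimates positively correlated. With equal arms and one control group used in full by every comparison, the correlation is 0.5, and 0.0195 takes full credit for that.

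Personalised randomisation removes part of the sharing. Only four-way TURP men enter all three comparisons. The correlation falls as men choose two- and three-way schemes, and the chance of at least one false non-inferiority conclusion rises above 5%. The family-wise error rate is a stated property of the confirmatory test, so it should be one that the design has.

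A related point concerns reporting. A non-inferiority result is commonly read by comparing the upper confidence limit with the margin. The unadjusted 95% interval tests at a different level from the p-value rule, so the two can disagree.

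**Working it through.** **Inputs.** From sections 10.2 and 10.3.1: three comparisons, one-sided level 0.0195, margin 3, SD 6.3, true difference 0, 100 evaluable per arm. From sections 7.2.1 and 10.2: the schemes, equal allocation and the pooling table. Assumed: normal estimates with equal variances, each comparison estimated from its own pool, equal arm sizes within a scheme after attrition, no allowance for inverse probability weights or site effects.

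**1. Reproducing the protocol's figures.** The critical value for 0.0195 is c = 2.064. With common correlation ρ, and all three true differences at the margin,

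FWER(ρ) = 1 − ∫ φ(u) · Φ[(c − √ρ·u)/√(1 − ρ)]³ du.

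At ρ = 0.5 this is 4.98%. The exact one-sided Dunnett value at ρ = 0.5 is 2.062, or p = 0.0196. So 0.0195 is correct, very slightly conservative, for a fully shared control. The sample size also reproduces: 100 per arm gives power 90.1% (noncentral t); 100/0.75 rounds up to 134; 4 × 134 = 536.

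**2. Correlation under the pooling rule.** Let W be the number of TURP men in one comparison (taken as equal for all three) and S the number shared by two comparisons. Each estimate has variance 2σ²/W, and two estimates have covariance σ²S/W². Hence ρ = 0.5 × S/W. Any two comparisons share the four-way scheme and one three-way scheme; each also uses a second three-way scheme and its own two-way scheme.

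Even choice over the seven TURP schemes (assumption): per participant, the schemes yield 1/4, 1/3 or 1/2 TURP men.
- S is proportional to 1/4 + 1/3 = 0.583
- W is proportional to 1/4 + 1/3 + 1/3 + 1/2 = 1.417
- ρ = 0.5 × 0.583/1.417 = 0.206

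**3. Family-wise error at 0.0195.**

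| Scheme mix among the TURP schemes | ρ | FWER |
|---|---|---|
| All four-way | 0.5 | 4.98% |
| 50% four-way, 25% three-way, 25% two-way | 0.34 | 5.32% |
| All three-way | 0.25 | 5.48% |
| Even over seven schemes | 0.21 | 5.54% |
| All two-way | 0 | 1 − (1 − 0.0195)³ = 5.74% |

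The error passes 5% once ρ falls below about 0.49, which requires almost all TURP men to be four-way.

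**4. Threshold that would hold 5%.** At ρ = 0.25, 0.0177; at ρ = 0.206, 0.0175; at ρ = 0 (Šidák), 1 − 0.95^(1/3) = 0.01695, about 0.0170. At 0.0170 and 100 per arm, power is 89.0% (noncentral t). About 103 per arm (normal approximation) or 104 (noncentral t) restores 90%.

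**5. Interval and test.** A two-sided 95% interval tests at one-sided 0.025. The two-sided level matching 0.0195 is 1 − 2 × 0.0195 = 96.1%; for 0.0170 it is 1 − 2 × 0.0170 = 96.6%. A result with p between 0.0195 and 0.025 has an upper 95% limit below 3 yet fails the test. With standard error 6.3 × √(2/100) = 0.891, the chance of this per comparison is about 1.7% at a true difference of 0 and 4.0% at 1 point.

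**The case against.** The strongest reply is that the arithmetic is right on its own terms and the excess is slight. The protocol says that it assumes a Dunnett correction, and 0.0195 does give 4.98% under that assumption. The worst case needs every man in the TURP comparisons to be in a two-way scheme and all three treatments to sit exactly at the margin. Expected uptake of the schemes is nowhere stated, so no single figure between the limits can be claimed. All of this stands. It limits the size of the point and makes it a mismatch between assumption and design. It does not rescue the word maximum, because the assumption conflicts with the pooling table in the same section. The supplementary analysis that pools all 11 schemes could share TURP men more fully, but it is not the confirmatory test.

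On intervals, a reader might infer that neither reported interval matches the test. The documents do not support that. It is shown for the unadjusted 95% interval only. The adjusted interval's construction is not given: as a two-sided Dunnett interval it would test at 0.0094 and not match, but as one-sided 95% Dunnett bounds it would test at 0.0196 and match in practice. Leaving that construction to the SAP is normal.

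A reader might also compute a family-wise error of 6.3–7.3% from the unadjusted intervals. That is the error of a rule the protocol does not use; section 10.3.1 decides on the p-value.

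**Conclusion.** The 5% maximum in sections 10.2 and 10.3.1 is true only if essentially all TURP men serve all three comparisons (correlation about 0.49 or more). Under the protocol's own pooling rule the family-wise error at 0.0195 lies between 4.98% and 5.74%, depending on a scheme mix that the document does not give. It is therefore right to say that 5% may be exceeded, by up to 0.74 percentage points, and not that it will be exceeded by any particular amount. The limits rest on the normal, equal-variance approximation; weighting, site effects or unequal loss between arms would shift the correlation somewhat.

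The interval point is secondary: the unadjusted 95% interval does not correspond to the 0.0195 test, and no interval is named as the one to read with the decision.

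The point is worth correcting because it concerns a stated property of the confirmatory test and the correction is cheap. It does not threaten the trial's conclusions in general.

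**What to change.** Choose one of the following before outcome data are unblinded.

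1. **Realised overlap.** Specify that the threshold is computed from the multivariate normal distribution with the correlation implied by the TURP participants actually shared (for example, 0.0175 at correlation 0.21). This needs counts by scheme and arm, not I-PSS results. Section 10 already provides a blinded methodology advisor who could approve it.
2. **Šidák.** Use 0.0170, which takes no credit for shared controls. Carry the unrounded 0.01695, since 1 − (1 − 0.0170)³ is 5.01%. Power at 100 per arm falls from about 90% to 89%.
3. **Keep 0.0195** and correct both sentences to say that the maximum is about 5.0–5.7%, depending on scheme choice.

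In each case, build the adjusted interval already promised in section 10.3.1 to match the final threshold (96.1% two-sided at 0.0195; 96.6% at 0.0170), and name it as the interval read against the margin of 3. The unadjusted 95% interval can still be reported beside it.

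The cost is a protocol amendment to sections 10.2 and 10.3.1, plus SAP wording. No change to data collection is needed. Under option 2, full 90% power would take about 103–104 evaluable men per arm instead of 100, although section 10.2 already expects baseline adjustment to lift power above 90%.

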10.3.2. Analysis of the Secondary Outcome Measures

Secondary efficacy outcomes will be analysed for superiority of each experimental treatment against control. For each pairwise comparison data will be pooled across randomisation schemes as shown in Section 10.2. Estimated differences between treatment groups will be reported with 95% confidence intervals and two-sided p-values. Analyses will primarily be performed in the per-protocol population (with IPW used where required). Analyses may also be repeated using alternative analysis populations.

Secondary patient-reported outcome measures (including ICIQ-MLUTS — voiding score and incontinence score, ICIQ-MLUTSsex total score, ICIQ-LUTSqol total score, I-PSS-QOL score) up to three years will be analysed using similar linear mixed-effects regression models as described above for the primary outcome measure, but with the baseline value corresponding to the relevant questionnaire included as a fixed effect rather than the baseline I-PSS. Additional scores or items from patient-reported outcome measures may also be reported and analysed using suitable mixed-effects regression models.

Bladder voiding efficiency (BVE) and maximum flow rate (Qmax) at 12 months will be analysed using a linear mixed-effects models, including site as a random effect (this will be the Hub where a Hub and Spoke model is used) and treatment group, randomisation scheme, and baseline measures of the outcome variable of interest as fixed effects.

Length of hospital stay will also be analysed using a linear mixed-effects models, including site as a random effect and treatment group and other stratification factors as fixed effects.

Duration of perioperative catheterisation will be measured as the time from intervention to stopping catheter use. Where a catheter is not required this will be set to zero. Data will be analysed using either a Cox proportional hazards or linear regression model with mixed-effects (including site as a random effect and treatment group and randomisation scheme as fixed effects), depending on whether any censoring is present.

The proportion of participants requiring a blood transfusion will be analysed using a mixed-effects logistic regression model, including site as a random effect and treatment group and randomisation scheme as fixed effects.

The proportion of participants requiring a readmission, experiencing acute urinary retention, requiring a catheter, or re-intervention during follow-up will be analysed using mixed-effects logistic regression models, including site as a random effect and treatment group and randomisation scheme as fixed effects. Time to readmission, catheterisation, acute urinary retention or re-intervention may also be analysed using a Cox proportional hazards model, depending on the number of events observed. Where there are multiple incidences of these outcomes per participant, the data may also be analysed using suitable models for count data, as appropriate for the distribution of the data. Further details will be provided in the statistical analysis plan.

Safety outcomes, including early post-operative symptoms and post-surgical complications will be analysed in the safety population according to the intervention received. Complications will be tabulated by type and severity, with the number and proportion of participants affected and the total number of occurrences reported.

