	To compare the use of and duration of catheterisation perioperatively and post-intervention	Perioperative and post-intervention catheterisation duration and subsequent use of catheters up to three years post-intervention
	To compare the hospital attendance rate post-intervention	Number and rate of hospital attendances (in patient or outpatient visits) for events/conditions possibly associated with BPE, condition progression, intervention, (including routine follow-up appointments post-intervention) or treatment failure up to 12 months post-intervention
	To compare the blood transfusion rate post-intervention	Number of patients requiring blood transfusions up to six weeks post-intervention
	To compare the incidence of acute urinary retention post-intervention	Number of patients experiencing post- intervention acute urinary retention up to 12 months post-intervention
	To compare the surgical re-intervention rate	Number of patients requiring surgical re-intervention of any type for their urinary symptoms up to 3 years post-intervention
Secondary Economic	To estimate and compare costs and quality of life following intervention over 12 months	Average healthcare costs per participant over 12 months post-intervention for each area of resource use
		Utility scores derived from responses to the EQ-5D-5L questionnaire at baseline, six weeks post-intervention, six months and 12 months post-intervention
		Average QALYs per participant at 12 months post-intervention

	To compare the cost effectiveness of the interventions at two years and three years post-intervention	Incremental cost per quality-adjusted life year (QALY) gained at two and three years post-intervention Cost- effectiveness acceptability curves to assess the probability of each of the interventions being considered cost-effective at different WTP thresholds for a gained QALY at two and three years post-intervention
	To model costs and quality of life over a patient's lifetime	Average healthcare costs per participant over their lifetime
	To model the incremental cost per QALY over the patient's lifetime	ICERs and CEACs derived by extrapolating costs and QALYs from the data observed during the trial
	To estimate the net benefit value of the interventions for each individual	Participants' willingness to pay for each intervention or combination of interventions Incremental net benefit of interventions

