4. TRIAL DESIGN

Multi-arm, multi-centre, open-label, non-inferiority, personalised randomised controlled trial with a six-month internal pilot with defined progression criteria. In total, a minimum of 536 participants will be recruited and followed up for three years post-intervention.

Patients who are willing to receive at least two of the four trial interventions can be randomised among treatments they are willing to receive. There are 11 possible randomisation schemes for patients to choose from. (See section 7.2.) Site staff will be counselled to retain equipoise between all four interventions and should not aim to influence the participants choice for the interventions they are willing to receive. To mitigate against surgeon influence the pattern of participant choice will be monitored across sites.

All sites will offer all interventions. In some sites this may be through the use of a Hub and Spoke model, which functions by allowing patients to access a variety of treatments within their locality but not necessarily in their originating hospital or trust. Where this is the case trial participants may receive their study intervention at another hospital or trust, referred to as a 'Spoke' site. The 'Hub' site will be responsible for organising and conducting all study visits, (apart from the study

intervention as detailed above), collecting all study data, communicating with trial participants and liaising with the site/trust carrying out the study intervention as required.

By the nature of the different delivery of treatments and the need to record treatment-specific operative parameters and resource use, blinding of the participant, surgeon, clinical team, Health Economics and TMG is not possible.

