7.4. Participant Pathway

Following randomisation patients will need to wait (as per standard NHS waiting lists) to have their intervention. The waiting times may vary for different interventions and could be up to a year for TURP. Trial staff will ensure administration of the allocated treatment and participants will undergo the planned treatment within their local site hospital or spoke site. Participants will undergo postprocedural follow-up as per standard care, with a discharge letter being sent to the designated lead research team within the participant's local site hospital or hub site (as applicable) once the patient is discharged from hospital following their surgical intervention. The local lead research team will coordinate the six week and six month telephone calls, the 12 months visit and the administration and data entry of patient reported outcome measure (PROM)s (where these are to be completed on paper) at these visits. The administration (and data entry where required) of the PROMs at the two and three year follow up visits and sending of gift vouchers following completion of these questionnaires may be performed by either the local research team or centrally by the NCTU team, where patients require paper questionnaires/vouchers to be sent. Consent will be sought to collect and securely hold participant names and contact details for these purposes. Follow-up timepoints will be measured from the date of intervention, (or in cases where the intervention does not take place, measured from the planned date). Participation will end and participants will resume standard clinical pathways three years from time of intervention. Depending on the date of their intervention some participants may only be followed up for two years.

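### Re-intervention and later catheter use are three-year outcomes, but their only firm analysis is a proportion over unequal follow-up, with no fixed horizon or censoring

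*Protocol*

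**What the plan says.** Protocol section 3 defines the re-intervention outcome as "Number of patients requiring surgical re-intervention of any type for their urinary symptoms up to 3 years post-intervention". It gives later catheter use the same three-year limit.

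Section 10.3.2 fixes the main model for both: "or re-intervention during follow-up will be analysed using mixed-effects logistic regression models". The terms are site, treatment group and randomisation scheme. A time-to-event analysis is optional: it "may also be analysed using a Cox proportional hazards model, depending on the number of events observed". Further detail is left to the SAP.

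On the length of follow-up, section 4 states: "In total, a minimum of 536 participants will be recruited and followed up for three years post-intervention". Section 7.4 qualifies this: "Follow-up timepoints will be measured from the date of intervention", and then "Depending on the date of their intervention some participants may only be followed up for two years". On waiting times it adds: "The waiting times may vary for different interventions and could be up to a year for TURP". It gives no wait for any MIT.

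**The concern.** A logistic model for any event during follow-up gives every man the same weight, whether he was observed for two years or three. Read literally, a man seen for two years without an event counts the same as a man seen for three years without one. The summary is then neither a two-year nor a three-year risk, and its value depends on the mix of follow-up lengths in each arm.

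If that mix is the same in every arm, the comparison is not distorted when hazards are equal, but the reported proportion still has no defined meaning. If the mix differs by arm, the arm observed for less time looks better. The follow-up clock starts at intervention and the two-year group is set by intervention date. A longer wait in one arm would therefore shorten observation in that arm. TURP is the only arm for which section 7.4 names a long wait, so any such bias would most plausibly run against the MITs, in a comparison that section 10.3.2 frames as a test of their superiority.

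Acute retention and hospital attendance, to which readmission belongs, have 12-month horizons in section 3. A two-year cut does not touch them.

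**Working it through.** **The plan's own figures.** The protocol gives no number for re-intervention, for catheter use, or for the share of men with two years only. Its primary-outcome sample size reproduces and is not in dispute. With margin 3, SD 6.3, one-sided 0.0195 and 90% power, the normal approximation gives 99 per arm, and the t distribution gives power 0.9006 at 100. Then 100/0.75 = 133.3, so 134 per arm, and 4 × 134 = 536. The 134 is used below.

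**Could follow-up be cut, and for whom?** The Trial Summary gives a 71-month trial period and section 10.5 gives 20 months of recruitment. Three years of follow-up is 36 months. With a 12-month wait, 20 + 12 + 36 = 68, which leaves 3 months for set-up and close-out. With uniform recruitment, the share cut to two years is

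f = 1 − (71 − overhead − 36 − wait)/20, bounded to 0–1.

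The overhead and the MIT waits are assumptions.

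| Overhead (months) | 3-month wait | 6-month wait | 12-month wait |
|---|---|---|---|
| 3 or less | 0% | 0% | 0% |
| 9 | 0% | 0% | 1 − 14/20 = 30% |
| 12 | 0% | 1 − 17/20 = 15% | 1 − 11/20 = 45% |

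**Spurious odds ratio with equal hazards.** Take a constant hazard h, the same in both arms. The expected proportion with an event is

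P(f) = (1 − f)(1 − exp(−3h)) + f(1 − exp(−2h)).

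Section 2 gives an iTIND retreatment rate of 6.2% at two years, so h = −ln(0.938)/2 = 0.0320 and the three-year risk is 1 − exp(−0.0960) = 9.15%.

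- 30% of TURP men and 0% of MIT men cut: TURP 0.7 × 9.15 + 0.3 × 6.2 = 8.3%, MIT 9.2%. Odds ratio 1.12.
- 45% v 0%: TURP 0.55 × 9.15 + 0.45 × 6.2 = 7.8%, MIT 9.2%. Odds ratio 1.19.
- 45% v 15%: TURP 7.8%, MIT 0.85 × 9.15 + 0.15 × 6.2 = 8.7%. Odds ratio 1.12.
- 30% v 30%: 8.3% in both arms. Odds ratio 1.00.
- Extreme, 100% v 0%: 6.2% v 9.2%. Odds ratio 1.53.

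**False-positive rate.** For unadjusted proportions with n = 134 per arm, z = (P_MIT − P_TURP)/√[P_TURP(1 − P_TURP)/n + P_MIT(1 − P_MIT)/n]. The two-sided 5% rejection rate is 1 − Φ(1.96 − z) + Φ(−1.96 − z). At 30% v 0%, z = 0.0089/0.0344 = 0.26 and the rate is 5.8%. At 45% v 0%, z = 0.0133/0.0340 = 0.39 and the rate is 6.8%.

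**Other event rates, 30% v 0% to 45% v 0%.** Section 2 gives 2.5% to 9% for PUL without a horizon; these are treated here as two-year rates, which is an assumption. The 20% row is also assumed, to represent a commoner event such as catheter use.

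| Two-year rate | Odds ratio | False-positive rate |
|---|---|---|
| 2.5% | 1.11–1.18 | 5.3–5.7% |
| 6.2% | 1.12–1.19 | 5.8–6.8% |
| 9% | 1.12–1.19 | 6.1–7.6% |
| 20% | 1.14–1.22 | 7.5–10.9% |

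A common 24-month window, or a time-to-event model with administrative censoring, gives a ratio of 1.00 in every one of these cases.

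**The case against.** **The SAP may settle it.** Section 10.3.2 defers detail to the SAP, and the coding of men without a year-three visit is the kind of detail that belongs there. This stands in part: the protocol does not say whether such men count as event-free or as missing. But the model itself is already fixed, and a SAP that follows it inherits the problem. Counting two-year men as event-free misstates their three-year status, and setting them to missing throws away two observed years.

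**A Cox model is already named.** It is, but as an extra, and its trigger is the number of events. For perioperative catheter duration, the same section lets the choice between Cox and linear regression depend on whether any censoring is present. That is the right trigger, and it is not applied to the outcomes for which section 7.4 predicts shortened follow-up.

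**A reader might infer that the two-year men will be mostly TURP men, so that bias against the MITs is certain.** The protocol does not support this. A year is the stated upper limit of the TURP wait, not its typical value. No MIT wait is given, and two-year follow-up is tied to the date of intervention, not to the arm. The 30% to 45% v 0% splits need every TURP man to wait the full year, MIT men to wait much less, and 9 to 12 months of overhead. With 3 months or less of overhead nobody is cut.

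**A reader might also infer that this is the main durability outcome, or that this odds ratio drives the economic model.** The protocol says neither. Section 10.3.7 says only that trial data will be the model's main source.

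**The effect is small.** That stands. At the iTIND rate, the spurious difference of 0.9 to 1.3 percentage points is about one to two men in 134.

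**Conclusion.** The point holds in a limited form. The firm analysis of two three-year outcomes ignores follow-up length, although the protocol itself expects some men to have only two years. Whatever the waits, the resulting proportion does not estimate a defined risk.

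Bias against the MITs is conditional on TURP men waiting longer. Under the splits assumed above it is modest: an odds ratio of about 1.12 to 1.19 and a false-positive rate of about 6% to 7% at the iTIND rate, and none with equal shares. These sizes rest on a constant and equal hazard, uniform recruitment, assumed overhead and waits, 134 men per arm and an unadjusted comparison. Because the distortion comes only from third-year events, it would be smaller if events cluster soon after surgery and larger if failures come late.

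The difference between sections 4 and 7.4 is a matter of wording: a general plan and an exception stated openly elsewhere. It should be reconciled, but it is not a separate defect. The change is worth making because it costs little; the trial's primary conclusion is not at risk.

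**What to change.** 1. For re-intervention and catheterisation, make time to first event, censored at last completed follow-up, the main analysis. Use the Cox model already named, with site and randomisation scheme, or an interval-censored version where only the interval between visits is known. Give unequal follow-up as the reason, and drop the dependence on event count.
2. Alternatively, analyse the proportion in a common 24-month window and take three-year results from time-to-event estimates, so that the third year is not lost.
3. Make sure the date of re-intervention, or at least the visit interval, is recorded. The diary (section 7.3) and the re-intervention question (section 7.5.5.10) ask for details but do not name a date. Catheter dates are sought where possible (section 7.5.5.12), and after month 12 contact is yearly (section 7.12).
4. Report follow-up time by arm.
5. Reconcile the three-year statement in section 4 with section 7.4.

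The cost is a change of wording in section 10.3.2 and the SAP, a little more analysis work and one date item. The sample size and visit schedule do not change.
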